3.4.1 Data Collection

All data collection will occur via password-protected and HIPAA compliant data entry and management software, Research Electronic Data Capture (REDCap). Potential participants will be given unique study IDs at the outset of recruitment that will be used throughout the study to minimize use of identifiers. Only authorized study personnel will have access to files that link study IDs to identifiable data.

3.4.2 Adverse Events Definition and Reporting

Because the trial will not directly intervene on the clinical care of participants but will rather offer suggestions for care of participants with regard to pain management and opioid stewardship to a given participant's medical team, we anticipate that the risk for adverse events that are attributable to participation in the clinical trial will be minimal. We will monitor all participants during their participation in the trial for (1) death, (2) development of an adverse reaction to a recommended intervention (e.g., new medication) requiring medical care, and (3) increases in pain assessed via the numeric rating scale (standard hospital practice) requiring a change in medical care. We will notify the Yale HIC of these adverse events, and any other anticipated adverse events, immediately upon notification of the PI and will provide written documentation within 5 days.

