1.5 Potential Risks and Benefits

1.5.1 Potential Risks

Opioid Stewardship Intervention: The goal of the enhanced opioid stewardship intervention is to manage chronic pain while reducing risk of inappropriate/risky opioid use and preventing harms of opioid use. We anticipate no significant adverse effects from participating in the opioid stewardship intervention. It is important to note that the intervention team will not have a direct impact on patient care; all guidance related to appropriate pain management and adjuvant therapies will be provided to a participant’s clinical team, who will be ultimately responsible to decide whether to apply such guidance to their patient’s care. Nonetheless, there is a small chance that efforts to manage pain in the context of best practices for opioid use may inadvertently and temporarily result in distress in

participants. Distress may include temporary increases in pain or physical or mental discomfort from opioid withdrawal symptoms. All patients will receive best practice treatment for their withdrawal symptoms and treatment of OUD, if present, as part of usual clinical care.

Rating scales and questionnaires: Rating scales and questionnaires are all non-invasive, however, some questions may be distressing to participants.

Confidentiality: There is a small risk of a breach of data or private information associated with participation in this study.

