3.4 Study Procedures

All patients will receive standard hospital care. Patients who are identified as eligible for the study via screening in Epic will be approached during hospitalization, undergo informed consent, and be enrolled in the study. Those who consent will be asked questionnaires

related to patient reported outcomes of pain, anxiety, depression and quality of life at baseline. Patients will then be randomized on a 1:1 ratio to either the enhanced opioid stewardship program arm or a control (i.e., usual care) arm. Patients who are randomized to the intervention arm will have their medical record reviewed by both a pharmacist and a physician trained in pain and addiction medicine. The pharmacist and physician will provide best practice guidance via an Epic note to the primary care teams to consider, versus continuation with their usual care plan. All guidance will be voluntary for clinical teams to follow. All participants will be tracked daily in Epic for discharge status, and when discharge within 48 hours is anticipated, the study team will perform the final patient interview, which will be very similar to the baseline interview and composed of questionnaires related to pain, anxiety, depression, and quality of life. Medical record abstraction will be performed to abstract relevant characteristics of each participant's hospitalization, use of guideline-based best practices for pain management and opioid stewardship at discharge, and incidence of readmissions and ED visits within 30 days after discharge for the hospitalization during which the participant was recruited.

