3.5 Study Schedule

The total number of visits as part of this intervention will include (1) screening and consent, (2) baseline interview (may be combined with consent visit, per participant's preference), and (3) a peri-discharge interview (within 48 hours of anticipated discharge). The total number of study visits is expected to be three per participant, with the potential for greater frequency of interaction via phone. Each visit will last approximately 30 minutes or less.

Study Schedule:

Study Activity	Time frame/duration
1. Currently hospitalized patients screened in Epic	Every weekday
2. Eligible participants approached by study team	Every weekday
3. Study described, questions answered, written informed consent obtained	30 minutes
4. Participant completes baseline interview; \$25 gift card provided	15 minutes
5. Participant randomized to intervention or usual care arm	1 minute
6. Participant's hospitalization tracked for anticipated discharge status	Daily
7. Intervention participants' charts reviewed by study team's addiction medicine physician/pharmacist for adherence to best practice guidelines for pain management/opioid stewardship.	Once, within 24 hours of randomization
8. Study addiction medicine physician composes note in intervention participant's medical record with recommendations to optimize guideline-based pain management/opioid stewardship	Once
9. Study addiction medicine physician alerts primary clinical care team via Mobile Heart Beat of Epic note regarding guideline-based care recommendations	Once
10. Final participant interview performed within 48 hours of anticipated discharge; \$25 gift card provided	15 minutes
11. Medical record abstraction performed for hospitalization characteristics, use of guideline-based best practices for pain management/opioid stewardship, and readmissions/ED visits within 30 days	1-30 days post-discharge

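### Opioid withdrawal is named as a possible effect of the guidance, but the plan sets no common rule for finding it in both arms

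*Combined protocol and SAP*

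**What the plan says.** Section 1.5.1 accepts a small chance that managing pain under best practices may cause temporary distress: "Distress may include temporary increases in pain or physical or mental discomfort from opioid withdrawal symptoms". It adds that withdrawal will be treated within usual care.

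Section 3.4.2 sets out the safety monitoring: "We will monitor all participants during their participation in the trial for (1) death, (2) development of an adverse reaction to a recommended intervention" that needs medical care, and (3) "increases in pain assessed via the numeric rating scale (standard hospital practice) requiring a change in medical care". The HIC is to be told of these events "and any other anticipated adverse events, immediately upon notification of the PI".

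The guidance goes to one arm. Section 3.4 says "Patients who are randomized to the intervention arm will have their medical record reviewed by both a pharmacist and a physician", and the schedule in 3.5 has the matching step, "Study addiction medicine physician composes note in intervention" participants' records. Chart abstraction, by contrast, covers everyone. Section 3.4 says "Medical record abstraction will be performed to abstract relevant characteristics of each" participant's hospital stay, and item 11 of the schedule reads "Medical record abstraction performed for hospitalization characteristics, use of guideline-based best practices for pain management/opioid stewardship, and readmissions/ED visits within 30 days".

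**The concern.** Of the two kinds of distress named in 1.5.1, pain becomes a monitored event and withdrawal does not. Opioid dependence is an entry criterion, so withdrawal can occur under usual care as well as after a recommended change. If cases come to light mainly through the second event in 3.4.2, they will come from the intervention arm, with no control figure found by the same rule. A few such cases could make the program look harmful when it is not, or leave a real signal that nobody can interpret.

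The stake is modest. The pilot is about feasibility, clinical teams may decline the guidance, and the protocol calls the risk small. But section 4.15 intends the results as preliminary data for grants and for a manuscript, and safety information by arm is useful for both.

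**Working it through.** The plan gives no figure to reproduce; 3.7.2 states that there are no power calculations. The check is therefore mainly a comparison of texts.

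**Where withdrawal could be captured**

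| Place | Covers withdrawal? | Same rule in both arms? |
|---|---|---|
| 3.4.2, event 1 (death) | No | Yes |
| 3.4.2, event 2 (reaction to something recommended) | Yes, if it follows a recommendation and needs care | On the natural reading, no: only the intervention arm gets study recommendations |
| 3.4.2, event 3 (pain on the rating scale) | No; pain only | Yes, from routine hospital scores |
| 3.4.2, catch-all clause | Arguably yes, since 1.5.1 anticipates it | Open to both arms, but it starts only when the PI is told; no definition or search |
| 4.4, unanticipated problems | Only if unexpected in nature, severity or frequency, and raising risk | Open to both arms, but again a reporting duty |
| 3.2.2, outcomes | Not named | – |
| 3.6.3, interviews | Not named (pain, depression, anxiety, satisfaction) | – |
| 3.4 and 3.5, chart abstraction | Not named; hospitalization characteristics are not itemised | Done for all participants |

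The most specific route depends on arm. The routes open to both arms have no case-finding rule. The one procedure applied alike to everyone, chart abstraction, does not name withdrawal.

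**What a common item could show**

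Input: about 50 per arm (3.3.1). The event counts below are illustrative assumptions, because the documents give no withdrawal rate.

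Exact (Clopper-Pearson) 95% intervals for one arm:
- 0/50: upper limit 1 − 0.025^(1/50) = 7.1%. The one-sided 95% bound is 1 − 0.05^(1/50) = 5.8%.
- 2/50 (4%): 0.5% to 13.7%.
- 5/50 (10%): 3.3% to 21.8%.

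Newcombe 95% interval for the difference. With equal counts in the two arms, its half-width is √[(p − l)² + (u − p)²], where l and u are the Wilson limits:
- 2/50 in each arm: ±9.9 points.
- 5/50 in each arm: p = 0.100, l = 0.0435, u = 0.2136, so √(0.0565² + 0.1136²) = 0.127, or ±12.7 points.
- 10/50 in each arm: ±15.7 points.

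**A limit of the remedy: uneven charting**

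If the true rate p is the same in both arms, but a fraction s_i of cases is documented in the intervention arm and s_c in control, the false difference is p × (s_i − s_c). All three inputs are assumed. With s_i = 0.90:

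| p | s_c = 0.75 | s_c = 0.60 | s_c = 0.45 |
|---|---|---|---|
| 5% | 0.75 points | 1.5 points | 2.25 points |
| 10% | 1.5 points | 3.0 points | 4.5 points |
| 20% | 3.0 points | 6.0 points | 9.0 points |

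These figures caution against over-reading the new item. They do not measure harm from the present plan.

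**The case against.** The strongest reply is that participants are already protected. Section 1.5.1 anticipates withdrawal, so the catch-all in 3.4.2 takes it in for either arm once the PI knows of it, and treatment is promised to all. This stands. A reader might infer that withdrawal would go unreported; the documents do not support that. What is missing is a comparable count, not a duty to report.

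Second, a reader might infer that event 2 can never occur in a control patient. That goes too far. Section 3.4.2 says all participants are monitored and does not say who makes the recommendation, and sections 1.1 and 1.2 describe automated best-practice prompts in existing care. The study-only reading is the natural one, since the same paragraph speaks of the trial's own suggestions to the clinical team, but it remains an inference.

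Third, the abstraction forms listed in 4.6 are not in the documents, and the broad category of hospitalization characteristics might include withdrawal. This stands too. The point is that the written plan does not provide for the count, not that the count could not be obtained.

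Fourth, section 3.7 plans no table by arm for any monitored event, so withdrawal is one part of a wider silence. That is true, and this change does not cure it. Withdrawal still differs from pain and death in that its most specific route is tied to one arm.

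**Conclusion.** The point holds as a low-cost improvement. One of the two kinds of distress that the protocol itself names has no common case-finding rule, and the most specific route to it is, on the natural reading, open to the intervention arm only.

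The conclusion rests on that reading of event 2 and on the protocol text alone, without the abstraction forms. The size of any distortion under the present plan cannot be stated, because the documents give neither a withdrawal rate nor a rate of documentation.

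A reader might infer that the trial's efficacy or feasibility results are biased. The documents do not support this: withdrawal enters no primary outcome and no listed secondary outcome. Nor would the added item allow a test of safety between arms, given the interval widths above.

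**What to change.** Add one item to the chart abstraction already planned for every participant (3.5, item 11): clinician-documented opioid withdrawal requiring treatment or a change in medical care, from randomization to discharge, with onset date. Use the same definition in both arms, with no reference to a study recommendation. The clinical wording is for the investigators to settle. Report n/N by arm with exact 95% intervals, labelled as documented withdrawal, descriptively and without a test. Leave expedited reporting under 3.4.2 and 4.4 as it is.

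The cost is one item and a date on about 100 charts that will be opened anyway, with no new visit. It needs an approved IRB amendment (4.2). Because the catch-all in 3.4.2 is open-ended, the team should agree with the HIC that cases found only by routine abstraction are summarised, not expedited.

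The downsides should be stated with the result:
- The count is retrospective, since abstraction takes place 1 to 30 days after discharge, so it does not replace real-time monitoring.
- It covers the hospital stay only, although participation runs to 30 days after discharge.
- Charting is incomplete and may be fuller in the intervention arm, where a trained team reviews the records, so a small difference should not be read as an effect.

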3.5 Study Schedule

The total number of visits as part of this intervention will include (1) screening and consent, (2) baseline interview (may be combined with consent visit, per participant's preference), and (3) a peri-discharge interview (within 48 hours of anticipated discharge). The total number of study visits is expected to be three per participant, with the potential for greater frequency of interaction via phone. Each visit will last approximately 30 minutes or less.

Study Schedule:

Study Activity	Time frame/duration
1. Currently hospitalized patients screened in Epic	Every weekday
2. Eligible participants approached by study team	Every weekday
3. Study described, questions answered, written informed consent obtained	30 minutes
4. Participant completes baseline interview; \$25 gift card provided	15 minutes
5. Participant randomized to intervention or usual care arm	1 minute
6. Participant's hospitalization tracked for anticipated discharge status	Daily
7. Intervention participants' charts reviewed by study team's addiction medicine physician/pharmacist for adherence to best practice guidelines for pain management/opioid stewardship.	Once, within 24 hours of randomization
8. Study addiction medicine physician composes note in intervention participant's medical record with recommendations to optimize guideline-based pain management/opioid stewardship	Once
9. Study addiction medicine physician alerts primary clinical care team via Mobile Heart Beat of Epic note regarding guideline-based care recommendations	Once
10. Final participant interview performed within 48 hours of anticipated discharge; \$25 gift card provided	15 minutes
11. Medical record abstraction performed for hospitalization characteristics, use of guideline-based best practices for pain management/opioid stewardship, and readmissions/ED visits within 30 days	1-30 days post-discharge

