3.2.2 Secondary and Exploratory Outcome Variables (if applicable)

A secondary outcome for this pilot RCT will include a count of guideline-based care elements considered to be “best practices” for opioid stewardship in the setting of chronic pain. These include ordering of alternative pain relief medications (e.g., acetaminophen), ordering of a bowel regimen, ordering of medication to treat opioid use disorder, order of urine toxicology screen, ordering of ECG for patients prescribed methadone, avoidance of co-prescriptions of benzodiazepines, and other associate “best care” practices. These metrics will be abstracted from the medical record.

Other secondary outcomes will include pain frequency, intensity, and interference, assessed using a modified Brief Pain Inventory.¹ Depression and anxiety will be measured using the Patient Health Questionnaire-4.² Participant satisfaction with pain care will also be assessed

at discharge. ED visits and readmissions at the 30 days post-discharge from the hospitalization in which the participant is recruited will also be abstracted from the medical record.

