4.5 Data Quality Assurance

Data quality will be monitored via automated quality checks in REDCap and frequent review of data by the investigative team. All members of the investigative team will be trained in accurate data collection and reporting processes prior to the start of data collection.

Automated elements to be integrated into REDCap data collection forms include "response required" settings for critical data, out-of-range alerts for quantitative data, and "completion status" confirmation questions for all data collection forms. All data entry and modification will be tracked using automated audit trails. Data will be reviewed on a weekly basis by the investigative team for completeness and identification of possible out-of-range/extreme values.

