4.6 Study Records

Documents to be considered study records include: screening forms; enrollment forms; signed informed consent forms; baseline interview; final interview; guideline-based care notes from addiction medicine physician/pharmacist team; and post-discharge and 30-day medical record abstraction forms.

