4.7 Access to Source

Source data will be maintained per Medical Records policy in a password protected, secure, Health Insurance Portability and Accountability Act (HIPAA) compliant, web-based electronic database with a built-in audit trail, i.e., REDCap

Only Institutional Review Board (IRB) approved research team members who have current HIPAA and Collaborative Institutional Training Initiative (CITI) Good Clinical Practice (GCP) and human subjects protection training will be authorized to access records.

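### Does the day 1 to 30 abstraction window in the study schedule cut short the 30-day readmission and ED-visit outcome?

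*Combined protocol and SAP*

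**What the plan says.** Row 11 of the table in section 3.5 describes the activity as "Medical record abstraction performed for hospitalization characteristics, use of guideline-based best practices for pain management/opioid stewardship, and readmissions/ED visits within 30 days" and gives it a single time frame, "1-30 days post-discharge". The row therefore joins items that are settled by discharge (characteristics of the stay, use of best practices) to an outcome that accrues after discharge.

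The outcome is defined in two other places. Section 3.2.2 lists "ED visits and readmissions at the 30 days post-discharge from the hospitalization in which the participant is recruited" among the secondary outcomes, with the medical record as source. Section 3.4 calls it the "incidence of readmissions and ED visits within 30 days after discharge for the hospitalization during which the participant was recruited". Neither says on which day the chart is to be read.

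Section 4.6 names "post-discharge and 30-day medical record abstraction forms" among the study records: two forms, neither with a completion date. Sections 3.1.2 and 3.6.2 end each person's participation 30 days after discharge. On traceability, section 4.5 states that "All data entry and modification will be tracked using automated audit trails", and section 4.7 describes a "web-based electronic database with a built-in audit trail, i.e., REDCap".

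**The concern.** One time frame serves two kinds of item that need different timing. Index-stay items can be read from the chart at any time after discharge. A 30-day count is complete only when day 30 is over. If the cell means that abstraction may be done on any day from 1 to 30, then 29 of the 30 permitted days fall before the outcome window closes, and no permitted day falls after it.

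The cell cannot simply be the span of record to be searched, because the index-stay items in the same row come before discharge. For those items it has to be the period in which the work is done.

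At stake is the completeness of a secondary outcome. A form closed early with no event recorded looks the same as a form from a participant who had no event. The loss would therefore not show up as missing data, and the event frequency carried into the manuscript and later grant applications (section 4.15) would be too low.

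**Working it through.** The plan gives no figure of its own to reproduce, so the check is of the text, with one line of arithmetic.

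**Step 1: size of the loss for one form.** Inputs: an outcome window of 30 days (sections 3.2.2 and 3.4) and permitted abstraction days 1 to 30 (section 3.5, row 11). For a form completed at the end of day d and not reopened, unseen days = 30 - d.

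| d | Unseen days | Share of window |
|---|---|---|
| 7 | 30 - 7 = 23 | 23/30 = 77% |
| 14 | 30 - 14 = 16 | 16/30 = 53% |
| 21 | 30 - 21 = 9 | 9/30 = 30% |
| 30 | 30 - 30 = 0 | 0% |

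The last line matters most: the upper end of the permitted range already captures the whole window. The lack of a permitted day after day 30 costs nothing, apart from any delay in charting.

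**Step 2: size of the loss for the trial.** With k forms closed at day d and never reopened, unseen participant-days = k x (30 - d), out of 100 x 30 = 3,000. The documents give neither k nor any abstraction date. With k = 0 the loss is zero, and any other value would be a guess. No event rate is given either, so unseen days cannot be turned into lost events.

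**Step 3: which reading fits all the sections?** There are three candidates.

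- *Any item on any day from 1 to 30.* This fits the index-stay items. It conflicts with sections 3.2.2 and 3.4, because a reading on day 10 cannot give the outcome defined there, and it leaves the second form in section 4.6 without a purpose.
- *The span of record searched.* This fits the readmission and ED items but not the index-stay items.
- *Abstraction begins on day 1 with the post-discharge form and ends on day 30 with the 30-day form.* This fits the row, both outcome definitions and the two forms.

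Only the third reading satisfies every section. The table also supports it: its timing column is a summary that mixes frequencies, durations and ranges, so a range there more naturally shows when the work starts and ends than makes every day equally acceptable for every item.

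**Step 4: can an early form be found and put right?** Yes. Entries are date-stamped through the audit trail (sections 4.5 and 4.7), the source is a retained medical record, and readmissions and ED visits carry their own dates. A chart read too soon can be read again before analysis.

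**Step 5: what depends on it?** The primary outcomes in section 3.2.1 are screening, eligibility, enrolment, hospital day of enrolment, delivery of the intervention and completion of the peri-discharge evaluation. None uses this abstraction. The count of guideline elements concerns care up to discharge, so the day of reading does not alter it. Nothing ties the timing of abstraction to study arm.

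**The case for a change.** The strongest case for a change is that row 11 is the only place that times the abstraction, and that it allows the incomplete reading while leaving a reading on day 31 strictly off schedule. A form's name is not a waiting rule. The checks in section 4.5 (required fields, out-of-range alerts, completion status, weekly review for completeness and extreme values) would all pass a form closed on day 10 with no event. Section 3.7.6 applies no missing-data method, and the bivariate tests in section 3.7.3 make no allowance for unequal observation time. The audit trail could reveal early forms, but no section plans to look. Splitting one table row would be cheap.

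Part of this stands. No earliest date is written for the 30-day form, no check of its date is planned, and the listed quality checks would not detect an early one. The rest does not carry. The argument needs someone to complete a form labelled for 30 days well before day 30, against an outcome defined over 30 days, and then not return to the chart. The documents give no sign of that practice. Day 30 is on schedule and loses nothing, so the row does not shut out a complete reading. That an edit would be cheap does not show that it is needed.

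**Conclusion.** The wording is loose, but the plan needs no change. The outcome definitions in sections 3.2.2 and 3.4 and the separate 30-day form in section 4.6 supply what row 11 leaves out, and a study team would fill the gap in the obvious way: index-stay items from day 1, the 30-day form once the window has closed. On that reading the loss is zero outcome days per participant.

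This rests on two assumptions: that the 30-day form is completed at the end of the window, as its name implies, and that charting delay is negligible. If the first failed for some participants, each affected form would lose 30 - d days until the chart was reread, and the dated entries and retained record allow that before analysis. The result would be an under-count in one secondary outcome of a pilot that section 3.7.2 says was not powered for any effect size. The feasibility conclusions would stand.
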